Among the clinical studies conducted, those where the population is represented by diabetic individuals stand out, where hibiscus tea was administered (4 g. of hibiscus distributed in 4 intakes) was administered to elderly women with hypertension and diabetes (following their pharmacological treatment without modifications) which showed as a result the reduction of fasting blood glucose levels, which is attributable to the reduction of cortisol, it should be noted that this

hormone plays an important role in the homeostatic control of blood glucose by activating gluconeogenesis (Yusni & Meutia, 2020). On the other hand, Sarbini et al., (2019) presented contradictory results to the aforementioned, since the values of blood glucose, fasting insulin, and HOMA-IR, showed no significant differences between the placebo group and the HS group (administration for 8 weeks of 50 mg of pure extract in 2 capsules), although this is attributed to the consumption of antihypertensive drugs and failure in the effective dose. For this reason, it is preferable to perform clinical studies in apparently healthy people, in order to have a clearer answer about the hypoglycemic effect of hibiscus, without the intervention of pharmacological factors involved.

Similarly, Mayasari et al., (2018) focused their research on prediabetic women reporting the decrease in fasting blood glucose levels, after administration of Roselle-Stevia tea bags (5 g and 125 mg, respectively) twice daily for 14 days. Therefore, they assure that the amount provided is the effective dose for the reduction of fasting and two-hour postprandial glucose values in prediabetic individuals.

Likewise, several authors suggest that the antiglycemic effect provided by the existing compounds in hibiscus, may follow several mechanisms including inhibition of α -amylase and α -glucosidase enzymes, decrease of advanced glycation end products in plasma and reduction of oxidative stress caused by hyperglycemia (Bule et al., 2020), it is also able to increase insulin secretion and improve insulin resistance in diabetic individuals (Sarbini et al., 2019).

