The concept of the glycemic index has been expanded over the years, giving rise to mathematical products such as the glycemic load (GL), which is defined as the quantity and quality of carbohydrates consumed and estimates the total glycemic effect of the diet, for its obtaining it is necessary to multiply the amount of CHO contained in the food ingested by the GI value ($GL = GI \times \text{available carbohydrates}$).

The increase to the glycemic load is associated with an unfavorable physiological response, mainly for people living with diabetes, since blood glucose and insulin values rise sharply. Foods with $GL \leq 10$ are considered low GL and foods with $GL \geq 20$ are considered high GL.

OBJECTIVES

General objective

To evaluate the *in vivo* bioavailability of bioactive compounds from a *H. sabdariffa* beverage and their immunomodulatory potential against moderate inflammation caused by SARS-CoV2 as well as enzymatic inhibition of α -amylase and α -glucosidase enzymes *in vitro*.

Specific objectives

1. To perform HPLC-DAD-MS characterization of a *Hibiscus sabdariffa* hibiscus-based beverage.
2. To perform an acute single-blind clinical trial, administering a hibiscus drink to normal-weight adults.
3. To evaluate the bioavailability of organic acids and phenolic compounds in urine and plasma samples present in the *H. sabdariffa* beverage.
4. To evaluate the immunomodulatory potential of the metabolites identified as bioavailable in plasma samples.
5. To evaluate the enzymatic inhibition of α -amylase and α -glucosidase exerted by the digested, placebo and treatment beverages.
6. To evaluate the *in vivo* GR and IR of the placebo beverage and treatment beverage.

. GENERAL METHODOLOGY

First Stage

Obtaining hibiscus-based beverage and placebo.

The hibiscus-based beverages (H.sabdariffa) and placebo were obtained from the reformulated company NUTRIYÉ SAPI de CV, located in the city of Guadalajara, Jalisco, Mexico.

Participants.

Twelve normo-weight volunteer participants without any medical condition were included. The invitation to participate was made through ITESO's communications office, as well as through announcements in social networks. They were selected according to the following criteria:

Within the inclusion criteria to be considered are those mentioned in Table 4.2.

Table 4.2. Non-inclusion and inclusion criteria for volunteer selection.

Inclusion criteria		Non-inclusion criteria	

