Normolipidemia	Total cholesterol (plasma) < 200 mg/L-1	Hypertension	Hyperthyroidism
	Triglycerides < 150 mg/L-1	Diabetes	In diet
	Fasting glucose (plasma) < 100 mg/L-1	Smokers	Pregnant or lactating women
Normoglycemia	18.5 – 24.9	Cardiovascular disease	In medical treatment / supplements
BMI [kg/m2]	18 – 40	Secondary	Hepatic insufficiency

Abdominal circumference [cm].	Men < 90 Women < 80	hyperlipidemia Renal insufficiency	Infection / inflammatory disease (6 weeks prior to study)
Fat percentage [%] [cm]	Men < 19 Women < 33		
Systolic pressure [mmHg].	< 140		
Diastolic pressure [mmHg].	< 90		
Alcohol	Last consumption one week and a half		

The study adhered to the ethical principles for research on human subjects of the Declaration of Helsinki and was submitted to the ITESO Research Ethics Committee.

Acute Trial Clinical Intervention

An acute single-blind trial was conducted. Participants consumed a hibiscus-based drink (*H. sabdariffa*), or a 60ml placebo drink, and then received a Western-type diet characterized by excessive consumption of red meat, simple carbohydrates, ultra-processed products, colorants, saturated fats, refined sugars and very little intake of fiber and vitamins. After a washout period of more than 6 days, the participants underwent a second intervention with a different product from the first one (beverage to be evaluated or placebo, as appropriate), and the samples were repeated according to the following scheme

The protocol was previously explained to the volunteers and all those who give their written informed consent will be candidates to participate (Annex 1). On the day of the intervention, participants will arrive at 7 a.m., Mexico Central Time, with an overnight fast of 10-12h. They were requested a rest period of 30 min prior to blood pressure taking at the time of admission, in addition to the fact that they had to be seated, upright and with their feet on the floor during the process; the measurement was performed using a manometer on the left arm, elevated at the level of the heart (Gómez-León Mandujano et al., 2016).

Two types of sampling were performed:

(a) Urine.

For determination of phenolic compounds and organic acids in urine samples, a basal sample (T=0) was taken in a collection bottle. Once the hibiscus-based drink or placebo was ingested, samples were collected at the following times: 3h, 6h, 12h and 24h.

b) Blood

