Blood samples (approx. 250 μL , 4-5 drops) will be drawn through finger pricks (OneTouch Ultra® lancets). Measurements over time will be similar to the glycemic response assessment technique. Samples will be placed in BD Microtainer SST tubes and kept at room temperature for 30 min. Samples will then be centrifuged

(5000 rpm, 25°C) for 10 min to obtain serum and kept in a freezer at -20 degrees Celsius until further analysis (Hossain et al., 2021).

Serum insulin concentrations will be analyzed using a two-site solid-phase enzyme immunoassay kit (Human Insulin ELISA Kit, Millipore, EZHI-14K), where the direct sandwich technique is used with two antibody solutions targeting insulin epitopes (Figure 6. 2) in such a way that the plate will be coated with a monoclonal antibody (capture) and then the sample will be added, so that the analyte of interest (insulin) will bind with the capture antibody and subsequently a horseradish peroxidase-labeled detection secondary antibody will be added, this antibody will bind to the antigens that will be in turn bound to the capture antibody, consequently will be added the substrate 3,3',5,5'- tetramethylbenzidine in buffer (TMB), forming a bluish coloration dependent on the insulin concentration, the reaction will be terminated by the addition of stop solution (HCl) obtaining as colored product (yellow) after acidification, which is quantifiable at 450 nm in a microplate reader (BioTek®, Synergy HT, Winooski, Vermont, USA). The results will be expressed in $\mu\text{U/L}$.

Statistical Analysis.

Statistical analysis: first stage

The normality of the data distribution will be evaluated by means of the Shapiro-Wilk test; if so, a Student's t-test will be used, or, on the contrary, a nonparametric Mann-Whitney test will be used to evaluate the statistical differences between the variables. The level of statistical significance will be a value of ($p < 0.05$). Statistical analysis will be performed with the STATISTICA program, version 10 (Statsoft.1984-2011 Inc., Tulsa, OK, USA).

Statistical analysis: second stage

Each sample will be considered as an experimental unit. Statistical analysis will be performed with the STATISTICA program, version 10 (Statsoft. 1984-2011 Inc., Tulsa, OK, USA). Differences in the response variables in the samples will be evaluated through a repeated-means ANOVA analysis. The level of statistical significance will be a value of ($p < 0.05$).

Calculation of the area under the curve.

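### Neither analysis stage plans a hibiscus-minus-placebo estimate or interval, so with 12 participants a non-significant result can be misread as no effect

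*Combined protocol and SAP*

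**What the plan says.** Under Participants: "Twelve normo-weight volunteer participants without any medical condition were included". Under Acute Trial Clinical Intervention, each person takes both drinks: "After a washout period of more than 6 days", "the participants underwent a second intervention with a different product from the first one". The layout is therefore a two-period crossover, although the protocol does not use that word.

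Under Statistical Analysis, first stage, normality is checked with Shapiro-Wilk, and then "a Student's t-test will be used, or, on the contrary, a nonparametric Mann-Whitney test will be used". Whether the t-test is paired is not stated; Mann-Whitney is an unpaired test. Under second stage: "Each sample will be considered as an experimental unit", and "Differences in the response variables in the samples will be evaluated through a repeated-means ANOVA analysis". Each stage closes with "The level of statistical significance will be a value of ($p < 0.05".

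The section does not list which outcomes belong to which stage. The next section defines an area under the curve for glucose and insulin and discards area below the fasting level. Nothing in the documents specifies a between-drink difference, ratio, confidence interval, margin of relevance, power or sample-size rationale.

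The specific objectives are to evaluate bioavailability, immunomodulatory potential, enzyme inhibition, and the glycemic and insulinemic responses to the two drinks.

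**The concern.** A threshold on p answers whether a difference was detected. It does not say how large the effect of the drink is, or how large it could still be. With 12 people the gap matters in both directions. A null comparison of glucose, insulin, IL-6 or TNF-alpha could be taken as absence of effect when the data are also compatible with a reduction or a rise that someone would care about. A significant comparison would not, by the planned criterion alone, show how small the effect may be.

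The crossover exists so that each person serves as his or her own control. A Mann-Whitney comparison of the two sets of values ignores that pairing, and it is not tied to an estimate of the within-person difference.

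**Working it through.** **Inputs from the documents.** n = 12; each person takes both drinks; threshold 0.05. The sample size comes with no calculation, so there is no figure to reproduce.

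**Assumptions.** Two-sided test; all 12 complete both visits; paired analysis; no period or carry-over effect. The within-person CV is not in the documents, so a range of 10% to 35% is shown.

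**1. Precision without any CV.** Let SD_diff be the standard deviation of the 12 within-person differences.

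- Half-width of the 95% interval = t(0.975, 11) / √12 = 2.201 / 3.464 = 0.64 SD_diff. With a period term (10 df) it is still 0.64.
- An observed difference of zero leaves effects of up to 0.64 SD_diff in either direction inside the interval.
- A result just short of significance has an interval from about 0 to 2 × 0.635 = 1.27 SD_diff.
- Power from the noncentral t reaches 80% only for a true difference of 0.89 SD_diff. At 0.5 SD_diff it is 35%, so such an effect is missed about 65% of the time.

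**2. The same on a ratio scale (illustration).** s_w = √ln(1 + CV²); half-width on the log scale = 2.201 × s_w × √(2/12); limits at an observed ratio of 1.00 = exp(± half-width). The last column is exp(−2 × half-width), the lower limit when an observed reduction just misses significance.

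| Assumed CV | s_w | Half-width (log) | Limits at ratio 1.00 | Lower limit, just non-significant |
|---|---|---|---|---|
| 10% | 0.100 | 0.090 | 0.91-1.09 | 0.84 |
| 15% | 0.149 | 0.134 | 0.87-1.14 | 0.76 |
| 25% | 0.246 | 0.221 | 0.80-1.25 | 0.64 |
| 35% | 0.340 | 0.305 | 0.74-1.36 | 0.54 |

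Power for a true 20% reduction is 0.91, 0.53 and 0.31 at CV 15%, 25% and 35%, so it is missed in 9%, 47% and 69% of trials. For a true 30% reduction, power is 1.00, 0.90 and 0.65.

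**3. What pairing is worth.** In units of the SD of a single visit's value, an unpaired comparison of 12 with 12 values has a nominal half-width of t(0.975, 22) × √(2/12) = 0.85. The paired half-width is 0.635 × √(2(1 − ρ)), where ρ is the correlation between a person's two visits: 0.64 at ρ = 0.5 and 0.40 at ρ = 0.8. At ρ = 0 it is 0.90, slightly wider than the unpaired figure, so the gain depends on a correlation the documents do not give.

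**The case against.** The strongest reply is that this is generic reporting advice resting on assumed variability. Parts of it stand.

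- **Imprecision is not shown in absolute terms.** At CV 10% or 15%, an observed ratio of 1.00 would exclude a 20% reduction. A reader might infer that any null result here must leave a large effect open. The documents do not support that, because they give neither a CV nor a margin of relevance. Only the half-width in SD_diff units is free of the assumption.
- **How nulls will be read is not stated.** A reader might take the background on the hypoglycemic effect as proof that the investigators equate non-significance with no effect, since it says one trial "presented contradictory results to the aforementioned, since the values of blood glucose, fasting insulin, and HOMA-IR, showed no significant differences". But the same sentence attributes that result to antihypertensive drugs and an inadequate dose, and the text goes on to prefer studies in healthy people. It does not conclude that there is no effect. Misreading is a risk left open, not something the plan commits to.
- **Silence is not refusal.** Failing to plan an estimate does not mean that none will be reported. The plan also specifies quantitative outcomes: glucose in mg/dL, insulin concentrations, and areas under the curve. These describe the response to a drink, however, and not the difference between drinks.
- **The illustration models an analysis the plan does not state.** No log scale is mentioned, and because area below fasting is discarded, an incremental area can be zero and its log undefined. The ratio figures apply only where all values are positive.
- **The second stage may include the in vitro enzyme data,** where 12 participants are irrelevant. The point is confined to the human outcomes.

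None of this supplies the missing between-drink estimate or interval.

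**Conclusion.** The point holds in a limited form. The plan specifies tests at p < 0.05 and no treatment-effect estimate or interval, for a crossover whose objectives ask about the size of responses. Any non-significant paired result in 12 people leaves at least 0.64 SD_diff inside the 95% interval on one side, so it can be misread as no effect. That figure needs only n = 12, complete pairs and a two-sided 5% level. Its translation into percentages rests wholly on assumed CVs and runs from minor at 10% to substantial at 35%. Reporting the interval is how a reader would learn which case applies to each outcome.

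This should be changed before analysis. The data remain usable either way, but the planned criterion alone cannot say how large the effect of the drink is.

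**What to change.** In both stages, for the human outcomes, replace the p-only criterion with wording such as:

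> For each outcome, the within-participant hibiscus-minus-placebo difference (or the ratio, where all values are positive) is reported with its 95% confidence interval and a paired p value. Absence of a relevant effect is claimed only if the interval excludes a difference named by the investigators before analysis. Any other non-significant result is reported as inconclusive.

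Apply it first to glucose AUC, insulin AUC, and one summary each for IL-6 and TNF-alpha. The two cytokines are measured at eight times, so their summary must be named in advance. The paired analysis replaces the unpaired Mann-Whitney comparison; if the within-person differences are clearly non-normal, a Wilcoxon signed-rank test with its matching interval serves the same purpose.

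Cost: a few lines of analysis work, an extra column in the results tables, and a prior decision on the cytokine summaries and on a relevant difference for each outcome where absence of effect might be claimed. No new participants or samples are needed. The downside is that null results with wide intervals must be worded as inconclusive.

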Samples will be subjected to an in vitro digestion model adapted from the methodology by Blancas-Benitez et al., (2018). First, the samples will be subjected to an enzymatic hydrolysis process with pepsin at a temperature of 37°C for 1 h (step 1); the phenolic compounds (FC) released in the supernatant at this stage are considered as the FC present in the gastric fraction (GasF). Subsequently, the samples are hydrolyzed with pancreatin 5 mg/ml, P-1750, Sigma Aldrich) and α -amylase (120 mg/ml, A-6255, Sigma Aldrich) (step 2). The CF released at this stage of digestion is considered the CF present in the intestinal fraction (IntF).

α -amylase activity.

The products obtained from the various stages of sample digestion will be used to determine the α -amylase enzyme activity (U/mL) using the kinetic method proposed in the specifications of the amylase activity assay kit (Sigma-Aldrich #MAK009), which consists of taking an aliquot of 50 μ L of the various samples and depositing them in a 96-well plate, then mixed with 100 μ L of master solution, previously prepared with 50 μ L of amylase assay buffer and 50 μ L of α -amylase substrate mixture, then incubated at 25°C and at minute 3, the absorbance at 405 nm is measured to obtain the initial time (T-initial) using the Synergy HT microplate reader (Biotek Instruments, Inc. , USA), readings will be taken every 5 min until the values of the samples approach that obtained at the highest concentration of the standard (20 nM/well) giving rise to the T-final. A calibration curve will be performed with Nitrophenol at concentrations of 4, 8, 12, 16 and 20 nM/well. One enzyme unit is the amount of amylase that cleaves ethylidene-pNP-G7 to generate 1 mM p-Nitrophenol per min. The enzyme activity will be expressed as percentage inhibition (I%) and determined with the equation (Eq 6.1):

$$I\% = \frac{(B \times \text{Factor de dilución})}{\text{Tiempo de reacción} \times V} \quad \text{Ec 4.1}$$

Where:

B refers to the amount of Nitrophenol generated, reaction time is the T-final minus T-initial in minutes and V denotes the volume of sample added to the well (μ L).

α -glucosidase activity.

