The inhibition of α -glucosidase of the beverages will be evaluated using the products of the different phases of the in vitro digestion and will follow the methodology described in the specifications of the α -glucosidase kit (Sigma-Aldrich #MAK123) where first 220 μ L of deionized water will be placed in a well of a reading plate and in another well 20 μ L of deionized water will be placed and 200 μ L of calibrator will be added to one of them. From the samples previously prepared in 50 mM phosphate buffer (pH 7.0) 20 μ L will be taken and placed in separate wells and 200 μ L of master solution will be transferred to each of them, the solution will be previously prepared with 200 μ L of p-nitrophenyl- α -D-glucopyranoside (NPG) buffer and 8 μ L of NPG substrate, then incubated at 37° C and absorbance will be measured at 405 nm using Synergy HT microplate reader

(Biotek Instruments, Inc., USA), the initial measurement (T-initial) will be read and after 20 minutes the final absorbance (T-final) will be taken.

The enzyme activity will be expressed in units per liter (unt/L) and calculated with the equation (Eq 6.2) where one enzyme unit is the amount of α -glucosidase that catalyzes the hydrolysis of 1 mM p -nitrophenyl- α -D-glucopyranoside per minute at pH 7.0.

$$\text{unt/L} = \frac{(\text{Abs final} - \text{Abs inicial})}{\text{Abs del calibrador} - \text{Abs del agua}} \times 250 \text{ unt/L} \quad \text{Ec 4.2}$$

Where:

Abs of the calibrator is the value for the calibrator at 20 minutes, Abs of the water represents the value of the water at 20 minutes and unt are units.

Evaluation of glycemic response.

To obtain the biological sample, a lancet will be used to puncture the thumb of the volunteer's finger and the sample will be collected on highly sensitive test strips for capillary glucose measurement of the OneTouch Ultra® System.

The portable system used for pre- and postprandial glucose measurement allows the monitoring of capillary glycemic response under experimental conditions for healthy subjects. With the use of this equipment, measurements will be obtained from t_0 (preprandial), and at 15, 30, 45, 60, 90 and 120 min (postprandial). The results will be expressed in mg/dL.

Insulin analysis.

Participants will be required to hold a hand warmer ($\sim 40^\circ\text{C}$) for 5 min before each capillary blood sampling, to stimulate peripheral blood flow.

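### The second-stage paragraph makes each sample the experimental unit beside a repeated-measures ANOVA and does not say which outcomes it covers; applied to the human glucose and insulin curves, the two instructions conflict.

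*Combined protocol and SAP*

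**What the plan says.** The paragraph headed Statistical analysis: second stage gives a unit rule, "Each sample will be considered as an experimental unit", and a method, "Differences in the response variables in the samples will be evaluated through a repeated-means ANOVA analysis". It names no subject and no within-subject factor. The first-stage paragraph above it offers Student's t or Mann-Whitney and does not mention pairing.

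Neither paragraph lists its outcomes. General Methodology has a First Stage heading but no heading for a second stage. The word sample has several uses: beverage material in the enzyme work ("Samples will be subjected to an in vitro digestion model"), and volunteers' finger-prick blood in the glycemic response and insulin sections.

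The only human design described is in Acute Trial Clinical Intervention. After a washout, "the participants underwent a second intervention with a different product from the first one", with the product described as "beverage to be evaluated or placebo, as appropriate". Specific objective 6 concerns the in vivo "GR and IR of the placebo beverage and treatment beverage". Glucose is measured before the meal and at six later times up to 120 minutes. For insulin, "Measurements over time will be similar to the glycemic response assessment technique". The AUC section follows the second-stage paragraph directly and names no test.

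**The concern.** A repeated-measures ANOVA needs a unit that is measured more than once. If every sample is its own unit, nothing is repeated, so the paragraph does not yield a single error term.

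This matters most for objective 6. If each participant takes both drinks, the drink is assigned to a participant-visit, and the seven values within a visit are not seven independent pieces of evidence about it. Treating them as independent gives the drink comparison the wrong error variance and far too many degrees of freedom. It also leaves stable differences between people in the error for drink-by-time, the test of whether the drink changes the shape of the curve.

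**Working it through.** The plan gives no degrees of freedom, power or variance for this analysis, so there is no figure to reproduce.

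**Inputs from the documents.** 12 participants (Participants); 2 drinks per participant (Acute Trial Clinical Intervention); 7 times per visit, baseline plus 6 (Evaluation of glycemic response); the same schedule taken for insulin; significance level 0.05. That the finger-prick curves come from these 12 people at these two visits is inferred.

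**Degrees of freedom.**
- Literal rule: 12 x 2 x 7 = 168 values per analyte. A drink-by-time ANOVA has 2 x 7 = 14 cells, so error df = 168 - 14 = 154. Without baseline: 12 x 2 x 6 = 144 values and 144 - 12 = 132 df.
- Participant as subject: drink is tested against participant-by-drink, (12 - 1)(2 - 1) = 11 df.

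**Assumed model.** Value = person + person-by-visit + residual, with variance shares P, V and E summing to 1. The documents give none of these. The literal analysis uses an error variance of about P + V + E = 1.
- Drink: true over assumed variance = 7V + E. The person component cancels because each person has both drinks. Above 1 the literal test is too liberal; below 1 it is too strict.
- Drink-by-time: true over assumed variance = E, which is below 1 whenever P or V is positive.

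**Simulation under no effect.** 20,000 runs per split, two-sided 5%, residuals independent over time:

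| P / V / E | 7V + E | Literal drink type I error | Drink-by-time ratio (E) |
|---|---|---|---|
| 0.7 / 0.02 / 0.28 | 0.42 | 0.6% | 0.28 |
| 0.6 / 0.05 / 0.35 | 0.70 | 2.7% | 0.35 |
| 0.3 / 0.05 / 0.65 | 1.00 | 5.2% | 0.65 |
| 0.5 / 0.083 / 0.417 | 1.00 | 5.4% | 0.42 |
| 0.2 / 0.05 / 0.75 | 1.10 | 6.4% | 0.75 |
| 0.1 / 0.05 / 0.85 | 1.20 | 7.3% | 0.85 |
| 0.5 / 0.2 / 0.3 | 1.70 | 14.0% | 0.30 |
| 0.4 / 0.3 / 0.3 | 2.40 | 21.1% | 0.30 |
| 0.3 / 0.4 / 0.3 | 3.10 | 26.7% | 0.30 |

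With the participant as subject, the drink test stays at 4.8-5.2% in all nine. The literal drink-by-time test has type I error of 0-2.3%.

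**Serial correlation.** Samples 15 to 30 minutes apart are unlikely to have independent residuals. With AR(1) residuals at rho 0.7 (assumed, equal steps), E is multiplied in the drink ratio by 1 + (2/7)(6 x 0.7 + 5 x 0.7^2 + 4 x 0.7^3 + 3 x 0.7^4 + 2 x 0.7^5 + 0.7^6) = 1 + (2/7)(9.196) = 3.63. At 0.3/0.05/0.65 the ratio becomes 7 x 0.05 + 0.65 x 3.63 = 2.71. The literal drink error then goes from about 5% to about 23% (normal approximation: two-sided tail beyond 1.975/sqrt(2.71) = 1.20). The literal drink-by-time test stays conservative.

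**If the second stage is in vitro only.** A digest can be a unit, so the calculation above does not apply. Human glucose, insulin and AUC then fall to the first-stage Student's t or Mann-Whitney, with no pairing stated, or to no test.

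**The case against.** Four objections carry weight.

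1. *The finger-prick curves are not placed in the crossover visits.* The acute-trial section lists urine and venous blood, the latter on a different schedule running to 6 hours. The capillary glucose and insulin sections are written separately. This stands as a caveat. The inference is strong, because only one human design is described and objective 6 compares the same two drinks, but the 11 df and the paired analysis depend on it. The conflict with repeated times does not.

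2. *The plan names a repeated-measures ANOVA, so the 154-df analysis may never be run.* This is fair. A reader might infer that the trial will analyse 168 independent values; the documents do not establish that. They give two instructions that cannot both be followed and do not say which prevails.

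3. *Sample may mean something else.* It may be a digest. In a text that appears to be translated, it may also be one drink given to one participant, which would make the unit the participant-visit. Either meaning removes the 154-df model. Neither is stated, which is why the word needs a definition.

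4. *The percentages rest on assumptions.* They do, both on the variance shares and on the residual structure. A reader might infer that the unit rule always inflates false positives, or might take from the table a variance ratio at which it is safe. Neither is supported: some splits give a test that is too strict, and the 5% result at 0.3/0.05/0.65 does not survive serial correlation. Power comparisons are left out for the same reason.

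**Conclusion.** The point holds conditionally. The second-stage paragraph contains a unit rule and a method that conflict if it governs the human curves, and the documents do not say whether it does. On that reading, with the curves taken at the two acute-trial visits, the plan points to two error terms for drink: 154 df or 11. The literal drink test's type I error is about 0.6% to 27% over the assumed splits with independent residuals, and higher with serial correlation. This range reflects the splits chosen and is not a bound. No direction can be claimed for drink without variances the documents lack. The literal drink-by-time test is conservative throughout.

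On the in vitro reading the unit conflict is absent, but objective 6 has no clearly assigned analysis. Both readings call for a correction. It should be made; confidence is medium because the scope and the visit structure are inferred.

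**What to change.** - State which outcomes each stage covers, and define sample.
- State whether the finger-prick curves are taken at the two acute-trial visits.
- For human outcomes, delete the sample-as-unit sentence. Name the participant as subject, with drink and time as within-subject factors, and test drink against participant-by-drink (11 df with 12 participants). Add a period term, leaving 10 df, only if both drink orders were used, which the text does not establish.
- Apply a Greenhouse-Geisser correction to time and drink-by-time, or use an equivalent mixed model with participant and participant-by-visit effects.
- Analyse AUC as one value per participant-visit, paired within participant.
- For the in vitro assays, name the independent digestion run as the unit and give the number of runs.

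The cost is wording only; no new data are needed. The drink p-value may become less favourable, and the sphericity correction costs some power with 12 participants.
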